6.2. Treatment Period

6.2.1. Visit 2, Day 1/Week 0 (Baseline)

- Administer patient-reported outcomes (PROs) including Patient Global Assessment (PtGA), Dermatology Life Quality Index (DLQI), EuroQol Quality of Life 5-Dimension 5-Level Scale (EQ-5D-5L), Hospital Anxiety and Depression Scale (HADS), and Patient-Oriented Eczema Measure (POEM);
- Obtain weight;
- Obtain pre-dose vital signs including pulse rate, sitting blood pressure, respiratory rate and oral or tympanic temperature (after at least 5 minutes of rest);
- Review eDiary Pruritus NRS, CCl , and PSAAD completion (in selected countries) and review eDiary procedures with subject as necessary;
- Review any changes in the subject's prior and concomitant medications and treatment information;
- Check subject's understanding of protocol guidance for the use of background topical therapy as described in Section 5.9.1, ensure subject adherence to background topical therapy requirements and re-educate as required;
- Conduct complete physical examination;

- Conduct clinical evaluations including Fitzpatrick Skin Type Assessment, IGA, SCORAD, EASI and BSA (calculated in the EASI);
- Perform a single 12-lead electrocardiogram (ECG). Clinically significant or exclusionary ECG findings require screen failure;
- Obtain samples for laboratory testing: serum chemistry, hematology (including coagulation panel), lipid profile (fasting), and urinalysis;

C

- Collect sample for viral surveillance: Herpes simplex virus (eg, Herpes simplex virus (HSV) HSV-1, HSV-2 and varicella zoster virus (VZV), etc);
- Urine pregnancy test (female subjects of childbearing potential). A negative urine pregnancy test must be obtained prior to dosing with the investigational product;
- Assess need for contraception and adherence to applicable lifestyle requirements (Section 4.4). Establish willingness and ability to comply with lifestyle requirements going forward in the study;
- Review of Inclusion/Exclusion Criteria:
- If subject continues to meet all Inclusion/Exclusion criteria, officially randomize subject into the study;
- Dispense oral investigational product to the subject;
- Administer oral investigational product and observe dosing;
- Dispense injectable investigational product to the subject;
- Unblinded administrator/trainer: administer the first dose of injectable investigational product, using this injection to train the subject and/or caregiver in the proper injection technique;
- Unblinded administrator/trainer: observe the administration of the second dose of injectable investigational product performed by the subject or his/her caregiver;

Assess and record any Adverse Events since the last visit.

6.2.2. Visit 3 (Phone call visit), Day 8/Week 1 (±1 day)

- Call subject and confirm compliance with daily completion of Pruritus NRS, and PSAAD (in selected countries);
- Verbally confirm subject has been compliant with study dosing and entry in the eDiary. Review eDiary procedures with subject as necessary;
- Review any changes in the subject's concomitant medications and treatment information;
- Check subject understanding of protocol guidance for the use of background topical therapy as described in Section 5.9.1 and re-educate as required;
- Assess need for contraception and adherence to applicable lifestyle requirements (Section 4.4). Establish willingness and ability to comply with lifestyle requirements going forward in the study;

• Assess and record any Adverse Events since the last visit.

6.2.3. Visit 4, Day 15/Week 2 (±1 day)

- Administer PROs including PtGA and DLQI;
- Obtain pre-dose vital signs including pulse rate, sitting blood pressure, respiratory rate and oral or tympanic temperature (after at least 5 minutes of rest);
- Review Pruritus NRS, ocl and PSAAD completion (in selected countries) and review eDiary procedures with subject as necessary. Instruct subject that Pruritus NRS and ocl will now be completed only at visits on site and in the eDiary and will no longer be completed on a daily basis at home;
- Review any changes in the subject's concomitant medications and treatments information;

- Check subject understanding of protocol guidance for the use of background topical therapy as described in Section 5.9.1, ensure subject adherence to background topical therapy requirements and re-educate as required;
- Conduct targeted physical examination;
- Conduct clinical evaluations including IGA, SCORAD, EASI and BSA (calculated in the EASI);
- Perform a single 12-lead electrocardiogram (ECG);
- Obtain samples for laboratory testing: serum chemistry, hematology (including coagulation panel), and urinalysis;

- Urine pregnancy test (female subjects of childbearing potential). A negative urine pregnancy test must be obtained prior to dosing with the investigational product;
- Assess need for contraception and adherence to applicable lifestyle requirements (Section 4.4). Establish willingness and ability to comply with lifestyle requirements going forward in the study;
- Review eDiary to assess completion;
- Perform drug accountability procedures;
- Dispense injectable investigational product to the subject;
- Unblinded administrator/trainer: observe the administration of injectable investigational product performed by the subject or his/her caregiver;
- Administer oral investigational product and observe dosing;

Assess and record any Adverse Events since the last visit.

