- For Japan only: In addition to HBsAg and HBcAb, HBsAb testing will be performed at Screening for all subjects rather than as a reflex test. Subjects with negative results for HBsAg, HBcAb and HBsAb may be eligible. Subjects who are HBsAg negative, HBcAb negative and HBsAb positive and provide documentation of prior HBV vaccination may be eligible and will not require HBV DNA monitoring during the study. Subjects who are HBsAg negative, HBcAb negative and HBsAb positive without documentation of prior HBV vaccination AND subjects who are HBsAg negative, HBcAb positive, and HBsAb positive at screening will have reflex testing for HBV DNA. Subjects who are HBV DNA negative or below LLQ may be randomized but will have HBV DNA repeated at Week 12 and Week 20 End of Treatment (EOT) visit, or Early Termination (ET) visit, whichever is sooner;
- Dispense eDiary and instruct subject in how to use the device. Instruct the subject to begin daily completion of the Pruritus and Symptoms Assessment for Atopic Dermatitis (PSAAD) (in selected countries), Pruritus NRS,
 - Pruritus NRS CCI will be collected daily in a subject eDiary during the screening period and from Day 1 to 15 and then on study visit days;
 - PSAAD will be collected daily in a subject eDiary during the screening period and from Day 1 through the End of Study visit, in selected countries;

• Instruct the subject to keep a daily record of use of standardized background topical therapy. Standardized background topical therapy use and adherence with guidelines will be recorded daily in the subject eDiary during the screening period and through the End of Study visit;

• If the subject is eligible for continued participation, provide subject with emergency contact card.

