- In Sequence A, if one hypothesis is not rejected at alpha level of 2.5% then no statistically significant will be claimed for any subsequent hypotheses in the sequence. In this case, the assessing for statistical significance in Sequence B will be at the 2.5% level. If all hypotheses in Sequence B are rejected, then the unused alpha level of 2.5% will be passed back for assessing the hypotheses in Sequence A at the 5% level. In Sequence B, if one hypothesis is not rejected at alpha level of 2.5 % then no statistically significant will be claimed for any subsequent hypotheses in the sequence.

Figure 2 Schematic for Multiple Testing Procedure

The figure above illustrates the procedure showing the sequence of the tests.

In order to be more rigorous about the onset of relief of severity of pruritus, a step-down approach with the NRS4 endpoint from Week 2 to earlier time points will be utilized as an additional family of hypothesis tests separate from [Figure 2](#) once statistical significance is demonstrated at Week 2. Rejection of each hypothesis of no difference in NRS4 at Week 2 within Sequence A will enable further assessing at earlier time points. Specifically, further hypotheses of no difference in NRS4 will be assessed along the following four sequences:

- If hypothesis of no difference in NRS4 at Week 2 between 200 mg QD and placebo is rejected in Sequence A, compare 200 mg QD versus placebo at Day 15, Day 14, Day 13, Day 12, ..., Day 2, in that order. Any hypotheses after the last time point (or Day) for which the comparison 200 mg QD versus placebo is significant will not be considered statistically significant.
- If hypothesis of no difference in NRS4 at Week 2 between 100 mg QD and placebo is rejected in Sequence A, compare 100 mg QD versus placebo at Day 15, Day 14, Day 13, Day 12, ..., Day 2, in that order. In this sequence, any hypotheses after the last time point (or Day) for which both comparisons (200 mg QD versus placebo and 100 mg QD versus placebo) are significant will not be considered significant.
- If hypothesis of no difference in NRS4 at Week 2 between 200 mg QD and dupilumab is rejected in Sequence A, compare 200 mg QD versus dupilumab at Day 15, Day 14, Day 13, Day 12, ..., Day 2, in that order. For this sequence, any hypotheses after the last time point (or Day) for which both comparisons (200 mg QD versus placebo and 200 mg QD versus dupilumab) are significant will not be considered significant.

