- If hypothesis of no difference in NRS4 at Week 2 between 100 mg QD and dupilumab is rejected in Sequence A, compare 100 mg QD versus dupilumab at Day 15, Day 14, Day 13, Day 12, ..., Day 2, in that order. For this sequence, any hypotheses after the last time point (or Day) for which all four comparisons (200 mg QD versus placebo, 200 mg QD versus dupilumab, 100 mg QD versus placebo and 100 mg QD versus dupilumab) are significant will not be considered significant.

All hypotheses in each of the four sequences will be assessed at the 5% level of significance. Although this testing procedure will not protect the Type-I error for the family of all possible comparisons, it will provide Type-I error protection for the family of NRS4 time points within each treatment group and treatment groups within each time point.

Hypotheses corresponding to all secondary and other endpoints will be tested at the 5% level of significance without any adjustment for multiplicity.

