Appendix 2. Definition and Use of Data Cut and Visit Windows in Reporting

For both the Week 16 Analysis and End of Study Analysis, a data cut at Week 16 drug dispensing visit will apply to each subject before the windowing. Only data from up to and including the Data Cut will be used for the Week 16 Analysis. Only data from after the Data Cut will be used for the End of Study Analysis. If a subject withdrew from the study and no drug was dispensed at Week 16, all available data for that subject will be included in the Week 16 Analysis.

Week 16 Analysis:

Visit Label	Target Day	Definition [Day window]
Screening		Days -28 to Day -1
Baseline	Day 1, Baseline	Day 1
Week 2	15	Days 2 to 22
Week 4	29	Days 23 to 43
Week 8	57	Days 44 to 71
Week 12	85	Days 72 to 99
Week 16	113	Days 100 to 120

End of Study Analysis:

Visit Label	Target Day	Definition [Day window]
Week 18	127	Days 121 to 134
Week 20	141	Days 135 to 155
Follow Up/End of Study		
Week 24	-	Days 156 to -

Visit windows will be used for efficacy variables, and for any safety data that display or summarize by study visit. For other endpoints (eg, ECG, vital signs), visit windows will be applied for summary statistics by study visits if required.

For the lab values, if the calculated study day for the labelled baseline visit is not study Day 1 but falls within 28 days before the start of the study dosing, then that data should be used for the baseline instead of leaving baseline missing.

For the other values, if the calculated study day for the labelled baseline visit is not study Day 1, but falls before the start of the study dosing, then that data should be used for the baseline instead of leaving baseline missing.

Observations on the actual day will be used to analyze Days 2-15 Pruritus NRS. Weeks 2, 4, 8, 16 Pruritus NRS will be based on the windowing method.

If two or more visits fall into the same window, keep the one closest to the Target Day. If two visits are equaled distant from the Target Day in absolute value, the later visit should be used.

Safety analysis may follow CaPS.

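### Protocol 6.1 and 6.2.3 disagree on whether a subject seen on Day 14 still records itch on Day 15, the first test in all four NRS4 onset sequences

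*Protocol*

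**What the plan says.** **Collection.** Protocol Section 6.1 (Screening) states that Pruritus NRS is collected daily in the eDiary during screening and then "from Day 1 to 15 and then on study visit days". Section 6.2.3 places Visit 4 at Day 15 with a window of ±1 day, so Days 14, 15 and 16 are all compliant. At that visit the site instructs the subject that the NRS "will now be completed only at visits on site and in the eDiary and will no longer be completed on a daily basis" at home. No exception is made for a visit on Day 14.

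**Analysis.** SAP Section 5.1 adds four step-down sequences for onset of itch relief, each opened by a significant Week 2 NRS4 result for the same comparison. The first reads "compare 200 mg QD versus placebo at Day 15, Day 14, Day 13, Day 12, ..., Day 2, in that order" and the last reads "compare 100 mg QD versus dupilumab at Day 15, Day 14, Day 13, Day 12, ..., Day 2, in that order"; the two between them also start at Day 15. On the level: "All hypotheses in each of the four sequences will be assessed at the 5% level of significance".

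SAP Appendix 2 fixes the data for each day: "Observations on the actual day will be used to analyze Days 2-15 Pruritus NRS". The Week 2 NRS value is instead taken from a window (Days 2 to 22), with the rule "If two or more visits fall into the same window, keep the one closest to the Target Day". Under SAP Section 5.3.1, a value missing intermittently in a subject who has not dropped out stays missing; it is not set to non-response.

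**The concern.** For a subject seen on Day 14 the two protocol instructions conflict. The one given in person, on the day, is the one that ends daily entry. If it is followed, the subject leaves the Day 15 analysis although still in the study and fully recorded up to Day 14.

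Day 15 is the entry point to the speed-of-onset claim. If a sequence fails there, none of Days 14 to 2 can be claimed in it. The sequences are also linked. The 100 mg versus placebo and 200 mg versus dupilumab sequences each also require 200 mg versus placebo to be significant at that day, and 100 mg versus dupilumab requires all four comparisons. A claim could therefore stop for lack of data on one day, because of visit scheduling.

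**Working it through.** **Inputs**
- Arm sizes: 200 per PF-04965842 dose, 200 dupilumab, 100 pooled placebo (Protocol 9.1).
- Week 2 NRS4: 18% on dupilumab and a 15-point difference, so 33% on PF-04965842; two-sided 5%; stated power at least 92% (Protocol 9.1).
- Phase 2b NRS4 at Day 15: 69.8% on 200 mg, 41.1% on 100 mg, 15.7% on placebo (Protocol 1.2.4).
- Assumed, because the documents give no share: 10%, 20% or 33% of Day 15 values lost. The 33% case corresponds to visits spread evenly over Days 14-16 with every Day 14 subject losing the value.
- Assumed: the Week 2 planning rates also hold at Day 15.

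**Formula.** Unstratified two-proportion z-test, n per arm, p̄ the pooled rate:

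power = Φ[(|p₂ − p₁| − 1.96·s₀)/s₁], with s₀ = √(p̄(1 − p̄)·2/n) and s₁ = √(p₁(1 − p₁)/n + p₂(1 − p₂)/n).

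The planned test is a CMH test stratified by baseline severity; the unstratified form is a close stand-in.

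**Step 1: the plan's own figure.** With n = 200 and p̄ = 0.255, s₀ = 0.0436 and s₁ = 0.0429. Then (0.15 − 0.0854)/0.0429 ≈ 1.50, and power is 93.4%. The stated figure of at least 92% reproduces.

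**Step 2: Day 15 with values lost (33% vs 18%).**

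| Share lost | n per arm | s₀ | s₁ | Power |
|---|---|---|---|---|
| 0% | 200 | 0.0436 | 0.0429 | 93.4% |
| 10% | 180 | 0.0459 | 0.0453 | 90.7% |
| 20% | 160 | 0.0487 | 0.0480 | 87.2% |
| 33% | 134 | 0.0532 | 0.0525 | 80.8% |

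**Step 3: chance of stopping at Day 15 once Week 2 has succeeded.** The two tests share most of their data, so stand-alone power overstates the added risk. This was simulated with a latent Day 14/Day 15 correlation of 0.9 (assumed). The Week 2 value was the Day 15 value or, if absent, the Day 14 value; Week 2 was tested at 2.5% and Day 15 at 5%. At 33% vs 18%, the chance that Day 15 fails given Week 2 success is about 2%, 5% and 11-12% for 10%, 20% and 33% lost. With complete Day 15 data it is about 1% or less.

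**Step 4: Phase 2b rates.** The same formula with unequal arms:
- 100 mg vs placebo (41.1% vs 15.7%): 99.8% with 200 and 100 subjects, 97.1% with 134 and 67.
- 100 mg at 41.1% vs dupilumab at the planning 18%: 99.9% with 200 per arm, 98.8% with 134.
- 200 mg at 69.8% vs either comparator: close to 100% with 33% lost.

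**Step 5: what is not touched.** A Day 14 value lies in the Week 2 window and is normally the value closest to Day 15 when no Day 15 entry exists, so the subject stays in the Week 2 key secondary analysis. Subjects seen on Day 15 or Day 16 lose nothing.

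**The case against.** The strongest reply is that no loss has been shown. A reader might infer that every subject seen on Day 14 has no Day 15 value. The documents do not support that: Section 6.1 calls for daily entries through Day 15, the diary instruction is given at screening, and nothing says that 6.2.3 overrides it. A subject who keeps to 6.1 will have the value. Section 7.10.1 also defers to the Schedule of Activities, whose NRS row carries its own footnote. That footnote is not visible in the public copy of either document and may resolve the conflict; its absence is not a fault of the plan. The eDiary settings are not shown either. All of this stands, and it limits the point to sites that apply 6.2.3 as written.

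The second reply is that the size depends on assumed shares and on an effect at the planning minimum. This also stands. The Phase 2b rates are the only observed Day 15 data in the documents. They may not carry over to this trial, but if they did, the loss of power would be small.

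Third, the onset sequences lie outside Figure 2, and the SAP itself says they do not protect the error rate over all possible comparisons. This is correct and lowers the stakes. The conflict remains: the two sections give incompatible instructions for a compliant visit, and no visible SAP rule lets Day 14 stand in for Day 15.

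**Conclusion.** The two sections conflict for a compliant Day 14 visit, and Day 15 values may be lost where 6.2.3 is followed literally. The consequence is a smaller Day 15 sample. A reader might infer bias, or damage to a key secondary result. Neither follows: the gap is tied to visit date and left missing, no link to outcome has been identified, and the Week 2 endpoint and Figure 2 family are intact.

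If 10%, 20% or 33% of values were lost, power at 33% vs 18% would fall from 93% to 91%, 87% or 81%. The chance of stopping at Day 15 after Week 2 success would be about 2%, 5% or 11-12%, against about 1% or less. These figures rest on the assumed shares, the planning-minimum effect and, for the stopping risk, the assumed correlation. The exposure is mainly in a dupilumab comparison with an effect near that minimum. Severity is low; this is a cheap improvement.

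**What to change.** Amend Protocol 6.2.3 to agree with 6.1: the subject continues daily home completion of Pruritus NRS through Day 15, even if the visit takes place on Day 14, and after that completes it only at site visits. Confirm that the eDiary ends daily prompts by study day and not by visit, and that the Schedule of Activities footnote says the same.

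The cost is one sentence, a check of a diary setting, and one extra diary entry for subjects seen on Day 14. Letting the Week 2 result replace the Day 15 step is not part of this fix: it would alter a pre-specified testing sequence for a loss not shown to occur.

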6.2.4. Visit 5, Day 29/Week 4 (±2 days)

- Administer PROs including PtGA;
- Review any changes in the subject's concomitant medications and treatments information;

- Obtain pre-dose vital signs including pulse rate, sitting blood pressure, respiratory rate and oral or tympanic temperature (after at least 5 minutes of rest);
- Review PSAAD daily completion (in selected countries), Pruritus NRS completion for this visit in the eDiary;
- Check subject understanding of protocol guidance for the use of background topical therapy as described in Section 5.9.1, ensure subject adherence to background topical therapy requirements and re-educate as required;
- Conduct targeted physical examination;
- Conduct clinical evaluations including IGA, SCORAD, EASI and BSA (calculated in the EASI);
- Perform a single 12-lead electrocardiogram (ECG);
- Obtain samples for laboratory testing: serum chemistry, hematology (including coagulation panel), lipid profile (fasting).
 and urinalysis;
- Urine pregnancy test (female subjects of childbearing potential). A negative urine pregnancy test must be obtained prior to dosing with the investigational product;
- Assess need for contraception and adherence to applicable lifestyle requirements (Section 4.4). Establish willingness and ability to comply with lifestyle requirements going forward in the study;
- Review eDiary to assess completion;
- Perform drug accountability procedures:
- Dispense oral investigational product to the subject;
- Administer oral investigational product and observe dosing;
- Dispense injectable investigational product to the subject;
- Unblinded administrator/trainer: observe the administration of injectable investigational product performed by the subject or his/her caregiver;
- Assess and record any Adverse Events since the last visit.

6.2.5. Visit 6, Day 57/Week 8 (±3 days)

• Administer PROs including PtGA;

- Obtain pre-dose vital signs including pulse rate, sitting blood pressure, respiratory rate and oral or tympanic temperature (after at least 5 minutes of rest);
- Review PSAAD daily completion (in selected countries), Pruritus NRS completion for this visit in the eDiary;
- Review any changes in the subject's concomitant medications and treatment information;
- Check subject understanding of protocol guidance for the use of background topical therapy as described in Section 5.9.1, ensure subject adherence to background topical therapy requirements and re-educate as required;
- Conduct targeted physical examination;
- Conduct clinical evaluations including IGA, SCORAD, EASI and BSA (calculated in the EASI);
- Perform a single 12-lead electrocardiogram (ECG);
- Obtain samples for laboratory testing: serum chemistry, hematology (including coagulation panel), GCI , and urinalysis;
- Urine pregnancy test (female subjects of childbearing potential). A negative urine pregnancy test must be obtained prior to dosing with the investigational product;
- Assess need for contraception and adherence to applicable lifestyle requirements (Section 4.4). Establish willingness and ability to comply with lifestyle requirements going forward in the study;
- Review eDiary to assess completion;
- Perform drug accountability procedures;
- Dispense oral investigational product to the subject;
- Administer oral investigational product and observe dosing;
- Dispense injectable investigational product to the subject;
- Unblinded administrator/trainer: observe the administration of injectable investigational product performed by the subject or his/her caregiver;
- Assess and record any Adverse Events since the last visit.

